3.2 Visit Schedule and Visit Windows

|  cros nt | | Forms | | | | | | | |
|--|--|--------------|------------------------------------|---------|--|----------------|--|--|---------|
| | | Title | Statistical Analysis Plan Template | | | | | | |
| | | Code | | Version | | Effective Date | | | Page |
| | | FRM_ST03_032 | | 01 | | 23 Apr 2015 | | | 9 of 31 |

Assessments and study visits will be performed as listed in the table below:

| Phase | Screening | Baseline ⁱ | Pre injection | Post injection | Telephone call ^a | Safety visits | | | | | Telephone call ^a |
|---|----------------------|-----------------------|---------------|------------------|-----------------------------|----------------|----------------|----------------|-------------------------|-------------------------|-----------------------------|
| Day | -14 to -up to dosing | -7 up to dosing | 0 | 0 | 1 | 2 +/- -1 | 7 +/- -1 | 14 +/- 1 | 21 ^l +/-1 | 28 ^h +/-1 | 40 |
| Electroretinography | | X | | | | | | X | | X | |
| Fluorescein angiogram | X | | | | | | | | | X | |
| Optical coherence tomography | | X | | | | X | X | X | X | X | |
| Best corrected visual acuity (ETDRS) | X | X | | | | X | X | X | X | X | |
| Visual field (computerized, 30°) | | X | | | | | X | | | X | |
| Visually evoked cortical potential | X | | | | | | | | | | X |
| Intraocular pressure | X | X | | X ^b | | X | X | X | X | X | |
| Slit lamp examination ^c | X | X | X | X ^b | | X | X | X | X | X | |
| Dilated fundoscopy ^d | X | X | | X ^b | | X | X | X | X | X | |
| Study drug injection | | | | X | | | | | | | |
| Blood sampling for PK analysis | X | | | X ^{b,e} | | X | | | | | |
| Corneal endothelial microscopy | | X | | | | | X | | | X | |
| Fundus photography | | X | | | | | | | | X | |
| Amsler grid | | X | | | | X | X | X | X | X | |
| Urine pregnancy test (only for Austrian protocols) ^m | | | X | | | | | | | X | |
| Urine pregnancy test (only for Belgium, United Kingdom and Netherland protocols) ^m | | | X | | | | | | | X | |
| Medical and ophthalmic histories | X | X | | | | | | | | | |
| Vital signs ^f | X | X | X | | | X | X | X | X | X | |
| Twelve-lead electrocardiogram | X | | | | | | | | | X | |
| Laboratory assessments | X | | | | | | | | | X | |
| Patient-reported outcomes ^g | | X | | | | | | | | X | |
| Concomitant medication | X | X | X | | X | X | X | X | X | X | |
| Serious medical events | X | X | X | X | X | X | X | X | X | X | X |
| Adverse events | X | X | X | X | X | X | X | X | X | X | X |

ETDRS: Early Treatment of Diabetic Retinopathy Study; PK: Pharmacokinetic

a. Standardized questions including (but not limited to): pain, blurred vision, change in visual acuity, redness of the eye

b. Examination will be performed after administration of study drug

c. Conjunctiva, cornea, anterior chamber including grading of cells and haze (Standardization of Uveitis Nomenclature Working Group), lens (Lens opacities classification system II) and vitreal haze (Standardization of Uveitis Nomenclature Working Group)

d. Including slit lamp biomicroscopy of the fundus

e. Day 0 blood sample will be taken 4 h ± 1 h after injection

f. Blood pressure and heart rate

g. National Eye Institute Visual Functioning Questionnaire 25 (VFQ-25), SF36™ Health Survey Version 2 (SF-3 v2) and EuroQol-5 Dimensions Health Questionnaire (EQ-5D)

h: for visit 28 option to perform examinations to 2 consecutive days;

i: in case screening visit and baseline visit are on the same day (-7 up to dosing), examinations scheduled for both visits need only to be performed once and may be used for both study visits;

l: safety visit 21 is applicable only for subjects enrolled under Austrian and German protocols;

| Forms | | | |
|--------------|--|------------------------------------|----------------|
| Title | | Statistical Analysis Plan Template | |
| Code | | Version | Effective Date |
| FRM_ST03_032 | | 01 | 23 Apr 2015 |
| | | 10 of 31 | |

m: urine pregnancy test has been performed at different visits, depending on the protocol version. For subjects enrolled under German protocols (versions 2.0, 3.0 and 3.1) no pregnancy testing is done.

3.3 Sample size justification

Eighteen patients will be enrolled in the study. No power calculations will be performed and the sample size is based on the requirements of the study design.

3.4 Randomization and blinding

This is an open-label, non-randomized study. Patients will be assigned to the next available cohort as they are recruited to the study.

3.5 Efficacy endpoints

3.5.1 Primary endpoint

In this study to assess the safety and tolerability of ascending doses of PP-001, safety parameters (i.e., changes in clinical signs and symptoms from ophthalmic exam, and AEs), are the primary endpoints. Detailed ophthalmic examination will be used to determine efficacy and as a safety measure.

The primary efficacy variable is the best corrected visual acuity (ETDRS) change from baseline at day 14 and day 28.

3.5.2 Secondary efficacy endpoints

- Improvement of inflammation or of any other parameter determined at the ophthalmic examination following the injection of PP-001:
 - Vitreous haze, as graded by the ophthalmologist during Slit Lamp examination (classified according to Standardization of Uveitis Nomenclature Working Group). The scale is based on the following unit scale categorized as follows:

| | |
|------|---|
| 0 | No inflammation |
| +0.5 | Trace inflammation |
| +1 | Mild blurring of retinal vessels and optic nerve |
| +1.5 | Optic nerve head and posterior retinal view obscuration greater than +1, but less than +2 |
| +2 | Moderate blurring of optic nerve head |
| +3 | Marked blurring of optic nerve head |
| +4 | Optic nerve head not visible |

- Electroretinography
- Fluorescein angiogram

| Forms | | | |
|--------------|--|------------------------------------|----------------|
| Title | | Statistical Analysis Plan Template | |
| Code | | Version | Effective Date |
| FRM_ST03_032 | | 01 | 23 Apr 2015 |
| | | 11 of 31 | |

- Optical coherence tomography
- Visual field (computerized, 30°)
- Visually evoked cortical potential
- Intraocular pressure
- Slit lamp examination
- Dilated fundoscopy
- Corneal endothelial microscopy
- Fundus photography
- Amsler grid

3.6 Safety endpoints

The safety endpoints are the following:

- Adverse Events (AEs);
- Vital Signs (blood pressure, heart rate);
- Electrocardiogram (ECG);
- Laboratory parameters (hematology, biochemistry and urinalysis).

3.7 Other endpoints

The other endpoints are the following:

3.7.1 PK parameters

The concentration of PP-001 in plasma at Screening, 4 h ± 1 h after dosing and on Day 2.

3.7.2 Patient Reported Outcomes

Patient-reported outcomes will be assessed by using the following questionnaire:

- Visual Functioning Questionnaire 25 (VFQ-25);
- SF36™ Health Survey Version 2 (SF-36v2);
- EuroQol-5 Dimensions Health Questionnaire (EQ-5D).

4. Statistical Analysis

4.1 General

Descriptive statistics will be provided for all variables in the summary tables by cohorts (PP-001 0.3 µg, 0.6 µg and 1.2 µg) according to the type of variable summarized.

Quantitative variables will be summarised by using n, arithmetic mean, SD, median and range (minimum and maximum).

Categorical variables will be summarised by using frequency distributions and percentages.

| Forms | | | |
|--------------|--|------------------------------------|----------------|
| Title | | Statistical Analysis Plan Template | |
| Code | | Version | Effective Date |
| FRM_ST03_032 | | 01 | 23 Apr 2015 |
| | | 12 of 31 | |

Analysis will be performed on the treated eye only assuming that a patient is treated on one eye only.

The baseline used in the analysis for each variable is reported in the table below:

| Endpoint | Baseline |
|------------------------------------|----------------------------------|
| Electroretinography | Baseline (Day -7 up to dosing) |
| Fluorescein angiogram | Screening (Day -14 up to dosing) |
| Optical coherence tomography | Baseline (Day -7 up to dosing) |
| ETDRS | Baseline (Day -7 up to dosing) |
| Visual field | Baseline (Day -7 up to dosing) |
| Visually evoked cortical potential | Screening (Day -14 up to dosing) |
| Intraocular pressure | Baseline (Day -7 up to dosing) |
| Slit lamp examination | Baseline (Day -7 up to dosing) |
| Dilated fundoscopy | Baseline (Day -7 up to dosing) |
| Corneal endothelial microscopy | Baseline (Day -7 up to dosing) |
| Fundus photography | Baseline (Day -7 up to dosing) |
| Amsler grid | Baseline (Day -7 up to dosing) |
| Patient-reported outcomes | Baseline (Day -7 up to dosing) |
| Vital signs | Baseline (Day -7 up to dosing) |
| Laboratory assessments | Screening (Day -14 up to dosing) |

All endpoints data collected in the eCRF will be presented in the listings. PK endpoints will be listed as well.

No multiplicity adjustment will be implemented.

4.2 Analysis sets

4.2.1 Per-Protocol Analysis Set

The PP set will include all Safety Set patients who have no major protocol deviations, and who complete the study up to the end of the post-study assessments (including telephone call days).

4.2.2 Safety Analysis Set

The Safety set will include all patients who receive at least one injection of study drug. All analyses will be conducted in this population.

4.2.3 Pharmacokinetic Analysis Set

The PK set will include all Safety Set patients who have at least one evaluable pharmacokinetic sample.

4.2.4 Incorrect treatment allocations

| Forms | | | | |
|--------------|--|------------------------------------|----------------|----------|
| Title | | Statistical Analysis Plan Template | | |
| Code | | Version | Effective Date | Page |
| FRM_ST03_032 | | 01 | 23 Apr 2015 | 13 of 31 |

Not applicable.

4.3 Sub-group analyses

Not foreseen.

4.4 Covariates

Not foreseen.

4.5 Pooling of sites

Not foreseen.

4.6 Interim analyses

No interim analyses will be performed.

4.7 Handling of missing and incomplete data

Missing values will not be imputed. The number of patients with missing data will be presented under the “Missing” category, if present.

Only the non-missing values will be evaluated for computing summary statistics.

4.8 Changes in the planned analysis

The following change was implemented in this SAP with respect to the analyses planned in the protocol:

- As agreed with the Sponsor, the Intent-to-Treat Analysis set will not be used for the analysis and only the Safety set will be used for the primary analysis instead. Moreover, also the Per Protocol set definition have been updated accordingly.
- As agreed with the Sponsor, vitreous haze will not be considered as the primary endpoint but as secondary endpoint and the best corrected visual acuity (ETDRS) change from baseline at day 14 and day 28 will be considered as the primary endpoint instead.
- Any reference to dose 2.1 µg treatment group (cohort 4) has been removed from the analysis since it has been decided to close the study at cohort 3.
- No interim analyses will be performed.

4.9 Data Review Meeting

| Forms | | | |
|--------------|--|------------------------------------|----------------|
| Title | | Statistical Analysis Plan Template | |
| Code | | Version | Effective Date |
| FRM_ST03_032 | | 01 | 23 Apr 2015 |
| | | | 14 of 31 |

Major protocol violations will be identified by the Sponsor and provided to CROS NT in order to create the PP set.

4.10 Software

All statistical analyses and data processing will be performed using Statistical Analysis Systems (SAS®) Software (release 9.4) on a Windows 7 operating system.

5. Evaluation of Demographic and Baseline Characteristics

5.1 Subject enrolment and disposition

Statistical analysis

Disposition of patients will be presented by cohort and overall for all the patients..

The number of patients included in each of the Safety, PP and PK sets will be summarised for each cohort.

5.2 Protocol violations

Definitions and data conventions

All the protocol violations will be discussed case by case by the clinical team and the list of major and minor violators will be provided to CROS NT.

Statistical analysis

Major and minor protocol violations will be listed only.

5.3 Study discontinuations

Definitions and data conventions

Date of first study drug intake

The date of first study drug intake is assumed to be the date of the 1st injection at Day 0.

Completer/discontinued Patient

A Patient will be considered a completer if the answer to the question “Did the subject complete the study?” is equal to “Yes”.

A Patient will be considered as discontinued if the answer to the question “Did the subject complete the study?” is equal to “No”.

Statistical analysis

Patients who discontinued from the study prematurely will also be presented with a breakdown of the reasons for discontinuation by cohort and overall for the Safety set.

| Forms | | | |
|--------------|--|------------------------------------|----------------|
| Title | | Statistical Analysis Plan Template | |
| Code | | Version | Effective Date |
| FRM_ST03_032 | | 01 | 23 Apr 2015 |
| | | | 15 of 31 |

5.4 Demographics and baseline characteristics

Definitions and data conventions

Age

If the date of birth is not missing, age will be calculated using the following rules:

- If month of screening date is greater than month of date of birth or (month of screening date is equal to month of date of birth and day of screening date is greater than or equal to day of date of birth), then:

Age (years) = year (screening date) – year (date of birth)

- Otherwise:

Age (years) = year (screening date) – year (date of birth) - 1

In order to determinate the age of patient, the following rules will be applied for the partial date of birth:

- if only the day is missing, the 15th of the month will be assumed;
- if the day and the month are missing, 30th June will be assumed.

Body Mass Index (BMI) (kg/m2)

BMI will be calculated using the following formula:

$$\text{BMI} = \frac{\text{Body weight (kg)}}{\text{height (m)}^2}$$

Statistical analysis

The baseline demographic characteristics will be summarised for the single cohorts and overall by means of descriptive statistics.

The following characteristics will be provided for the Safety set:

- Age (years)
- Sex (male/female)
- Ethnicity (Hispanic or Latino/ Not Hispanic or Latino)
- Race (White, Black or African American, Asian, American Indian or Alaska Native, Native Hawaiian or other Pacific Islander)
- Weight (kg)
- Height (cm)
- BMI (kg/m²)
- Smoking Status (Non-smoker, Ex-smoker, Current smoker)

5.5 Medical and ophthalmic history

Definitions and data conventions

Past disease

| Forms | | | |
|--------------|--|------------------------------------|----------------|
| Title | | Statistical Analysis Plan Template | |
| Code | | Version | Effective Date |
| FRM_ST03_032 | | 01 | 23 Apr 2015 |
| | | 16 of 31 | |

A disease is considered as past disease if it is not ongoing at screening visit (“ongoing” box is not ticked).

Concomitant disease

A disease is considered as concomitant disease if it is ongoing at screening visit (“ongoing” box is ticked).

Statistical analysis

Past disease and concomitant diseases will be coded using Medical Dictionary for regulatory activities (MedDRA) dictionary (version 19.0) and frequency distributions and percentages will be summarised by sequence for the Safety set by System Organ Class (SOC) and Preferred Term (PT). Counts will be given for both SOC and PT by subject. Subjects experiencing more than one past/concomitant disease event will be counted only once within each SOC and PT.

5.6 Prior and concomitant medications

Definitions and data conventions

The following categories of medications will be identified:

- previous medication (stop date \leq date of first study medication intake);
- concomitant medication (stop date $>$ date of first study medication intake or stop date ongoing/missing).

In case of missing or incomplete dates/times not directly allowing allocation to any of the two categories of medications, a worst-case allocation will be done according to the available parts of the start and the end dates. The medication will be allocated to the first category allowed by the available data, according to the following order:

- concomitant medication;
- previous medication.

Statistical analysis

Previous and Concomitant medications

Medications will be coded using WHO Drug Dictionary (WHO-DD), version 2016Q1 (1st Quarter of 2016), and the following Anatomical Therapeutic Chemical Classification (ATC) codes:

- Anatomical Main Group (ATC 1st level code);
- Chemical subgroup (ATC 4th level code);
- Preferred name.

Previous and concomitant medications will be summarized separately for Safety set by anatomical main group, chemical subgroup and preferred name by cohort.

Subjects experiencing more than one previous (or concomitant) medication within the same anatomical main group, chemical subgroup and preferred name will be counted only once.

5.7 Other baseline characteristics

Not foreseen.

| Forms | | | | |
|--------------|--|------------------------------------|----------------|----------|
| Title | | Statistical Analysis Plan Template | | |
| Code | | Version | Effective Date | Page |
| FRM_ST03_032 | | 01 | 23 Apr 2015 | 17 of 31 |

6. Evaluation of Treatment Compliance and Exposure

6.1 Compliance to study drug and treatment

Not foreseen.

6.2 Exposure to study drug

Not foreseen.

6.3 Evaluation of pharmacokinetics

The concentration of PP-001 in plasma will be measured in blood samples taken at Screening, 4 h \pm 1 h after dosing and on Day 2. Analysis will be performed on the PK set.

7. Evaluation of Efficacy

All efficacy endpoints will be presented in terms of descriptive statistics by cohort for the Safety set.

7.1 Analysis of primary endpoint

Definitions and data conventions

The primary efficacy variable is the best corrected visual acuity (ETDRS) change from baseline at day 14 and day 28.

Primary efficacy analysis

Analysis will be performed on Safety and PP sets.

The best corrected visual acuity (ETDRS) will be summarized by visits and cohort together with the change from baseline at each post-baseline visit by means of descriptive statistics.

7.2 Analysis of secondary efficacy endpoints

Definitions and data conventions

The following detailed ophthalmic examination will be used to determine efficacy:

Vitreous haze

- as graded by the ophthalmologist during Slit Lamp examination (classified according to Standardization of Uveitis Nomenclature Working Group)

Electroretinography

- Investigator's assessment

| Forms | | | | |
|--------------|--|------------------------------------|----------------|----------|
| Title | | Statistical Analysis Plan Template | | |
| Code | | Version | Effective Date | Page |
| FRM_ST03_032 | | 01 | 23 Apr 2015 | 18 of 31 |

Fluorescein Angiogram

- Investigator's assessment
- Hypofluorescence
- Hyperfluorescence

Optical Coherence Tomography

- Retinal thickness
- Cystoid spaces
- Subretinal Fluid
- Vitreoretinal interface abnormalities

Visual Field Measurement

- Mean deviation
- Pattern standard deviation
- Short-term fluctuation
- Corrected pattern standard deviation
- Investigator's assessment

Visually Evoked Cortical Potential

- Investigator's assessment

Intraocular Pressure

- mmHg
- Investigator's assessment

Slit Lamp Examination

- Lid
- Conjunctiva
- Cornea
- Anterior chamber
- Iris
- Lens
- Macula
- Optic nerve
- Vitreous haze

Dilated Fundoscopy

- Retinal Oedema
- Infiltration
- Vasculitis
- Retinal Ischemia
- Epiretinal Gliosis
- Vascular occlusion
- Hyperpigmentation
- Hypopigmentation
- Choroid Atrophy

Corneal endothelial microscopy

- Average cell area
- Cell density
- Investigator's assessment

| Forms | | | | |
|-------|--------------|------------------------------------|----------------|----------|
| Title | | Statistical Analysis Plan Template | | |
| Code | | Version | Effective Date | Page |
| | FRM_ST03_032 | 01 | 23 Apr 2015 | 19 of 31 |

Fundus photography

- Investigator's assessment

Amsler grid

- Investigator's assessment

Statistical analysis

Descriptive statistics will be presented by visit and for each cohort on the Safety set.

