7. ADVERSE EVENTS

An AE is any untoward medical occurrence in a patient or clinical investigation patient administered a pharmaceutical product that does not necessarily have a causal relationship with this treatment. An AE can therefore be any unfavourable and unintended sign (including an abnormal laboratory finding), symptom, or disease temporally associated with the use of an investigational product, whether or not related to the investigational medicinal product.

Any pre-existing conditions or signs and/or symptoms present in a patient before the start of the study (i.e., before informed consent) should be recorded as medical/surgical history. Any medical occurrences that are new or worsened from the time of informed consent and up to and including the final visit must be reported as AEs or SAEs. All AEs and SAEs must be recorded irrespective of whether they are considered drug-related.

Patients will be monitored throughout the study for adverse reactions to the study medications and/or procedures at each study visit. Questions will be posed in a non-leading manner so as not to bias the response. In addition to questioning at specific time points, patients will be encouraged to report any AEs spontaneously. Any patient with an AE, SAE or clinically significant abnormal laboratory test value will be evaluated by the Investigator, or a monitoring physician, and will be treated and/or followed up until the symptoms or values have resolved or are assessed as stable by the Investigator. A physician, either at the Investigative site or at a nearby hospital emergency room, will administer treatment of any SAEs. Where appropriate, medical tests and examinations may be performed to ensure that an AE has fully resolved.

Adverse events will be monitored throughout the study from the time a patient is consented through the final follow-up visit; SAEs are to be collected from the time of consent through to the follow-up visit. Whenever possible, a specific disease or syndrome rather than individual associated signs and symptoms should be identified by the Investigator and recorded on the patient's eCRF. However, if an observed or reported sign or symptom is not considered a component of a specific disease or syndrome by the Investigator, it should be recorded as a separate AE on the patient's eCRF.

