Each AE or SAE reported will be assessed for severity and the date and time of onset (if available), time relationship to dosing, duration and outcome of each event will be noted.

Laboratory abnormalities are not considered AEs unless they are associated with clinical signs and symptoms or require medical intervention. Clinically significant abnormal clinical laboratory findings or other abnormal assessments that are associated with the disease being studied, unless judged by the Investigator as more severe than expected for the patient's condition, or that are present or detected at the start of the study and do not worsen, will not be reported as AEs or SAEs.

The Investigator will exercise medical and scientific judgment in deciding whether an abnormal clinical laboratory finding or other abnormal assessment is clinically significant.

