10.2 Safety Data Monitoring Board

Safety will be assessed by monitoring the results of the ophthalmic examinations and AEs throughout the study. Risk assessments will be made by the SDMB after each cohort in written form and throughout the study based on the above. For details please refer to SDMB policy.

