9.3 Tables

The list of tables is provided here below:

| TABLE | TITLE |
|----------------|---|
| TABLE 14.1.1 | SUBJECT DISPOSITION / SUMMARY OF ALL SUBJECTS |
| TABLE 14.1.2.1 | PRIMARY REASONS FOR DISCONTINUATION FROM STUDY / SAFETY SET |
| TABLE 14.1.3.1 | ANALYSIS SETS / SAFETY SET |
| TABLE 14.1.4.1 | DEMOGRAPHIC CHARACTERISTICS / SAFETY SET |
| TABLE 14.1.5.1 | MEDICAL AND OPHTHALMIC HISTORY: PAST DISEASES / SAFETY SET |
| TABLE 14.1.5.2 | MEDICAL AND OPHTHALMIC HISTORY: CONCOMITANT DISEASES // SAFETY SET |
| TABLE 14.1.6.1 | PREVIOUS MEDICATIONS / SAFETY SET |
| TABLE 14.1.6.2 | CONCOMITANT MEDICATIONS / SAFETY SET |
| TABLE 14.2.2.1 | ETDRS SCORES DURING THE STUDY AND CHANGE FROM BASELINE / SAFETY SET |
| TABLE 14.2.2.2 | ETDRS SCORES DURING THE STUDY AND CHANGE FROM BASELINE / PP SET |

| Forms | | | | |
|--------------|--|------------------------------------|----------------|----------|
| Title | | Statistical Analysis Plan Template | | |
| Code | | Version | Effective Date | Page |
| FRM_ST03_032 | | 01 | 23 Apr 2015 | 30 of 31 |

| TABLE | TITLE |
|----------------|---|
| TABLE 14.2.3.1 | SLIT LAMP EXAMINATION DURING STUDY / SAFETY SET |
| TABLE 14.2.4.1 | FLUORESCEIN ANGIOGRAM, ETDRS, VISUALLY EVOKED CORTICAL POTENTIAL, INTRAOCCULAR PRESSURE AND DILATED FUNDOSCOPY DURING STUDY / SAFETY SET |
| TABLE 14.2.5.1 | ELECTRORETINOGRAPHY, OPTICAL COHERENCE TOMOGRAPHY, VISUAL FIELD, CORNEAL ENDOTHELIAL MICROSCOPY, FUNDUS PHOTOGRAPHY AND AMSLER GRID DURING STUDY / SAFETY SET |
| TABLE 14.2.6 | PATIENT- REPORTED OUTCOMES DURING THE STUDY AND CHANGE FROM BASELINE / SAFETY SET |
| TABLE 14.3.1.1 | SUMMARY OF TREATMENT EMERGENT ADVERSE EVENTS / SAFETY SET |
| TABLE 14.3.1.2 | TREATMENT EMERGENT ADVERSE EVENTS BY SYSTEM ORGAN CLASS AND PREFERRED TERM / SAFETY SET |
| TABLE 14.3.1.3 | TREATMENT EMERGENT SERIOUS ADVERSE EVENTS BY SYSTEM ORGAN CLASS AND PREFERRED TERM / SAFETY SET |
| TABLE 14.3.1.4 | TREATMENT EMERGENT ADVERSE DRUG REACTIONS BY SYSTEM ORGAN CLASS AND PREFERRED TERM / SAFETY SET |
| TABLE 14.3.1.5 | TREATMENT EMERGENT ADVERSE EVENTS LEADING TO DISCONTINUATION BY SYSTEM ORGAN CLASS AND PREFERRED TERM / SAFETY SET |
| TABLE 14.3.1.6 | TREATMENT EMERGENT ADVERSE EVENTS LEADING TO DEATH BY SYSTEM ORGAN CLASS AND PREFERRED TERM / SAFETY SET |
| TABLE 14.3.2.1 | HAEMATOLOGY RESULTS DURING THE STUDY AND CHANGE FROM SCREENING / SAFETY SET |
| TABLE 14.3.2.2 | BIOCHEMISTRY RESULTS DURING THE STUDY AND CHANGE FROM SCREENING / SAFETY SET |

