9.4 Figures

Figures not foreseen.

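### The SAP drops three safety summaries that protocol 9.6 promises without declaring it, and its text and table titles plan change from baseline for only one of 12 ophthalmic exams

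*SAP*

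**What the plan says.** **Adverse events and vital signs.** Protocol 9.6 commits to TEAEs by system organ class and preferred term (SOC/PT), by severity and by relationship. It also commits to the worst post-baseline vital-sign value and to the number and percentage of patients with potentially clinically significant vital signs. The protocol synopsis repeats the severity and clinical-significance items. SAP 8.1 plans overall counts that include severe AEs, plus SOC/PT tables for TEAEs, SAEs, adverse drug reactions (ADRs), discontinuations and deaths. SAP 8.3 plans vital signs and their change by visit. SAP 4.8 lists four departures from the protocol: the ITT set, the primary efficacy variable, cohort 4 and the interim analysis.

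**Ophthalmic exams.** SAP 3.5.1 states that "safety parameters (i.e., changes in clinical signs and symptoms from ophthalmic exam, and AEs), are the primary endpoints". SAP 4.1 says "The baseline used in the analysis for each variable is reported in the table below" and gives a baseline visit for 12 ophthalmic exams. SAP 7.1 plans change from baseline for best corrected visual acuity (BCVA). For the other exams SAP 7.2 says "Descriptive statistics will be presented by visit and for each cohort on the Safety set". The corresponding titles in SAP 9.3 follow the pattern "SLIT LAMP EXAMINATION DURING STUDY / SAFETY SET", whereas the BCVA, patient-reported, laboratory and vital-sign titles name a change or shift.

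**The concern.** The primary objective is the safety and tolerability of ascending single intravitreal doses. Two parts of the planned reporting fall short of it.

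First, the protocol promised a severity breakdown and two vital-sign summaries as tables. The SAP omits them and its list of changes is silent, so a reader of that list would assume that protocol 9.6 is intact. Severity matters particularly here. The stopping rule restated in SAP 3.1 counts patients with moderate or severe drug-related AEs, and no planned table distinguishes moderate from mild or crosses severity with relationship.

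Second, the endpoint is defined as change, but for 11 exams the planned summary describes each visit separately. AE tables fill this only in part. Protocol section 7 makes reportable "Any medical occurrences that are new or worsened from the time of informed consent", but exempts "other abnormal assessments that are associated with the disease being studied, unless judged by the Investigator as more severe than expected". In eyes with uveitis that exemption can cover ocular signs that matter.

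**Working it through.** The plan has no figure of its own to reproduce on this point, since neither document contains a power calculation. The check is a comparison of texts, followed by small enumerations.

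**1. Protocol 9.6 against the SAP**

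| Protocol 9.6 item | SAP text and table titles | Declared in SAP 4.8 |
|---|---|---|
| TEAEs by SOC/PT | Kept (8.1; Table 14.3.1.2) | not needed |
| By relationship | Kept as pooled ADRs: possibly, probably or definitely related (8.1; Table 14.3.1.4) | no |
| By severity | Overall severe-AE count only (8.1); none of Tables 14.3.1.2 to 14.3.1.6 is by severity | no |
| Vital signs and change by visit | Kept (8.3; Table 14.3.3.1) | not needed |
| Worst post-baseline vital sign | Absent | no |
| n (%) potentially clinically significant | Absent | no |

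One item is cut down and two are missing. None of the three is among the four declared changes.

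**2. What the stopping rule needs.** The AE limb of the rule requires more than half of a cohort. With four patients, 2/4 = 50% does not exceed half and 3/4 = 75% does, so the threshold is 3 patients.

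**3. What the planned AE counts show.** Suppose three of four patients each have one related, non-severe TEAE. The planned summary gives:
- TEAEs: 3 events in 3 patients
- ADRs: 3 events in 3 patients
- severe AEs: 0 events in 0 patients

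Each event may be mild or moderate, so 0, 1, 2 or 3 patients (0% to 75%) may have had a moderate related event. The same table fits a cohort below the threshold and one that reaches it.

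**4. Count of exams.** SAP 4.1 lists 12: electroretinography, fluorescein angiogram, OCT, BCVA, visual field, visually evoked potential, IOP, slit lamp, dilated fundoscopy, endothelial microscopy, fundus photography and Amsler grid. Text and titles plan change for BCVA only, which leaves 12 − 1 = 11. All 11 appear in Tables 14.2.3.1, 14.2.4.1 or 14.2.5.1.

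**5. What by-visit summaries lose (constructed values, not from the documents).** Take IOP in one cohort.
- Baseline {12, 14, 16, 18}: mean 60/4 = 15.0; SD = √(20/3) = 2.58; median 15; range 12 to 18.
- Day 28 {12, 14, 16, 24}: mean 66/4 = 16.5; SD = √(83/3) = 5.26; median 15; range 12 to 24.

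With n = 4 these statistics effectively return the four values. The minimum, maximum and median fix the sum of the middle two, and the SD fixes their difference. Only the pairing of baseline with Day 28 is lost. There are 4! = 24 pairings. The patient at 24 mmHg started at 18, 16, 14 or 12, a rise of 6, 8, 10 or 12 mmHg, with 6 pairings each. No other patient can rise by more than 16 − 12 = 4. The table therefore proves a rise of at least 6 mmHg but leaves open a doubling of that.

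For a graded item, take vitreous haze {1, 1, 2, 2} at baseline and {0.5, 0.5, 0.5, 2} at Day 28. The mean falls from 1.5 to 0.875. The one patient at grade 2 on Day 28 is unchanged in 12 pairings and one grade worse in the other 12.

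**The case against.** The strongest reply concerns the ophthalmic part. Protocol 9.4.1 names only TEAEs and vital signs as safety analysis variables, and protocol 9.8 promises descriptive statistics for efficacy endpoints. On that reading SAP 7.2 departs from no planned table. SAP 4.1 fixes a baseline for every exam and SAP 9.2 sets decimals for change from baseline, which suggests that change was intended somewhere. The table shells sit in an appendix that was not supplied and may contain the columns. All of this stands. It reduces the ophthalmic part to a mismatch between the endpoint as defined and the analysis as written.

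A second reply is that the data are not lost. Listings cover every exam, AE and vital sign, and three cohorts of four are quick to read. That is true, but a listing does not replace a summary that the protocol promised, nor the declaration of its removal.

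A third reply is that the numerical examples are invented. They are. They show what the summaries cannot distinguish and say nothing about how often it would happen.

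A reader might also infer that dose escalation runs without sight of moderate events or eye findings. The documents do not support this. Results are reviewed after each dosing day, and protocol 10.2 says "Safety will be assessed by monitoring the results of the ophthalmic examinations and AEs throughout the study", with a written risk assessment after each cohort. Severity is recorded for every event.

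**Conclusion.** The concern holds as a reporting gap that should be fixed. The firm part is the departure from protocol 9.6: severity is reduced to one overall count, two vital-sign summaries are missing, and none of the three is declared. The consequence is that moderate drug-related AEs can be found only in the listings, although the rule restated in SAP 3.1 counts them. That rule also has a limb for major safety concerns judged by the investigator, which no AE table could settle.

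The softer part is that 11 of 12 exams behind an endpoint defined as change have no change or shift planned in the SAP text or table titles. It rests on the unseen shells adding nothing. It does not support the claim that ophthalmic change will go unanalysed, or that a promised ophthalmic table was removed. Nor has the relationship breakdown been dropped, since it survives as pooled ADRs.

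**What to change.** 1. In SAP 8.1 and 9.3, add TEAEs by SOC/PT with maximum severity and by relationship. Give n/N per cohort with at least one moderate or severe related TEAE.
2. In SAP 8.3, restore the worst post-baseline vital signs, showing both highest and lowest, and the counts meeting the protocol Appendix 2 values. Apply posture-specific limits only where posture was recorded, because protocol 6.4 leaves measurement to site practice.
3. In SAP 7.2 and Tables 14.2.3.1 to 14.2.5.1, add change from baseline by visit and cohort for the numeric measures: IOP, retinal thickness, visual-field indices, and endothelial cell density and area. Include minimum and maximum change so that both directions show. Add baseline to post-injection shifts for vitreous haze and anterior chamber grades. Add shifts for other items only where the eCRF has ordered levels; the eCRF was not supplied, so this needs checking. Present these as descriptive safety summaries, without making every item a primary endpoint. If the shells already hold such columns, say so in 7.2.
4. Declare in SAP 4.8 anything that remains omitted.

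The cost is SAP and shell wording plus a few descriptive tables with small cells, from data already collected. No patients or visits are added. If the database is already locked, label the tables as added analyses.
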